#### **3.1.4. Treatment Period**

Patients meeting all eligibility criteria will receive 1 dose of study drug at 0.5 g/kg over 1 to 2 day(s), every 3 weeks (+/- 7 days) for a total of 16 doses.

Investigators or Study Nurses will call patients 4 days (+/1 day) after the end of each study treatment course to document potential AEs and TAEs (see Section [8.2.2](#)).

Duration of the treatment period will be approximately 45 weeks.

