### **3.1.6. Relapsing Patients**

A relapse is defined as one of the following conditions:

- Adjusted INCAT disability score increase by 1 point compared to baseline,  
AND  
Judging on the clinical examination and/or the neurological scales assessments, the Investigator considers change in patient's treatment is mandatory: increase in IVIg dosage, increase or initiation of a corticotherapy, immunosuppressive therapy, plasma exchange.
- Adjusted INCAT disability score increase by at least 2 points compared to baseline.

Relapsing patients will undergo the study assessments scheduled at the EOS visit within 7 days and prior to the administration of any other CIDP treatment. The patient will be then withdrawn from the study and treated at the discretion of his/her physician.

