## 2.5 EVALUATION CRITERIA

### 2.5.1 Primary Efficacy Criterion

The primary efficacy criterion is *response* at the End of Study (EOS) visit. A patient is defined as having a *response* (or being a *responder*) if both conditions below are fulfilled:

- The patient's adjusted inflammatory neuropathy course and treatment (INCAT) disability score did not increase by more than 1 between baseline and EOS visit.
- The patient's CIDP treatment was not changed between baseline and EOS visit.

A change in CIDP treatment is defined by any of the following conditions:

- Increase/decrease of the dose (g/kg) of the study treatment by 5%
- Decrease of the time between courses
- Addition of corticosteroids (equivalent of more than 10 mg/day of prednisone for more than 10 days) or immunosuppressive drugs. As this condition is not possible to derive by programming, the study physician will review all treatments with corticosteroids and immunosuppressive drugs prior to database lock and flag those who fulfil the condition
- Premature discontinuation of study drug due to insufficient response to IMP and start of other CIDP treatments such as IVIg (other than study drug), corticosteroids, immunosuppressive drugs or plasma exchange

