#### 4.5 COMPLIANCE

Study treatment compliance will be summarized using the TTS. Treatment compliance will be presented at the patient level as described below. The term *Planned* refers to the treatment dose and frequency planned at enrollment. The term *Prescribed* refers to the treatment dose and frequency reported at each IMP course and infusion.

Compliance will be described at the course level using the following criteria:

- Prescribed course dose (g/kg) = Theoretical course dose (g/kg)  
Theoretical course dose is defined according to the protocol as 0.5 g/kg.
- Time since previous course = 3 weeks  $\pm$  7 days
- Courses administered within 1 to 2 days
- Duration of the flow rate of the first course infusion remains unchanged for at least 25 minutes
- Flow rate of the first infusion of a course  $\leq$  0.5 mL/kg/h

Compliance will be described by patients using the following criterion:

- Total patient compliance: A patient is compliant if all courses of the patient are compliant.

Non-compliant courses and infusions will be listed by patient showing all of the above criteria. The criterion leading to non-compliance will be flagged.

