#### 4.6.1 Primary Efficacy Endpoint

The primary efficacy criterion is *response* of the patients at EOS visit. A patient is defined as having a *response* (or being a *responder*) both conditions below are fulfilled.

- The patient's adjusted INCAT disability score did not increase by more than 1 between baseline and EOS visit.
- The patient's CIDP treatment was not changed between baseline and EOS visit.

A change in CIDP treatment is defined by any of the following conditions:

- Increase/decrease of the dose (g/kg) of the study treatment by 5%
- Decrease of the time between courses
- Addition of corticosteroids (equivalent of more than 10 mg/day of prednisone for more than 10 days) or immunosuppressive drugs. As this condition is not possible to derive by programming, the study physician will review all treatments with corticosteroids and immunosuppressive drugs prior to database lock and flag those who fulfil the condition
- Premature discontinuation of study drug due to insufficient response to IMP and start of other CIDP treatments such as IVIg (other than study drug), corticosteroids, immunosuppressive drugs or plasma exchange

The primary analysis of the primary efficacy criterion will be done using the baseline and last available assessment of the adjusted INCAT disability score after the first study drug administration. That is, if the score at EOS visit is missing, then the Last Observation Carried Forward (LOCF) approach will be applied and the last available adjusted INCAT disability score will replace the missing value at EOS visit.

Similarly, if the assessment of the adjusted INCAT disability score is censored due to an intake of a forbidden treatment, the adjusted INCAT disability score from the last assessment before the intake of the forbidden treatment is used as replacement for the assessment of the EOS visit.

The number and percentage of Responders at EOS will be presented with descriptive statistics. The associated exact 95% Clopper-Pearson confidence interval (CI) will be calculated for the proportion of Responders.

The primary analysis will be performed using the FAS and a sensitivity analysis will be performed using the PPS.

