### 4.7.1 Extent of Exposure

#### Patient level analyses

The extent of exposure to IMPs will be summarized on the patient level using the following variables:

- Duration of study participation (m) from signing of informed consent to EOS: (EOS visit date – date of informed consent + 1) / 30.4375
- Duration of treatment exposure (m) from the first day of IMP administration to EOS: (EOS visit date – date of first IMP infusion + 1) / 30.4375
- Average course frequency:

$\frac{1}{n_c} \sum_{j=1}^{n_c} (\text{start date of course}_{j+1} - \text{start date of course}_j)$ , with  $n_c$  the number of courses of the patient

For the last course, the date of the EOS visit will be used as the *start date of course*  $n_c+1$ .

- Total number of courses
- Average number of infusions per course:  $\frac{1}{n_c} \sum_{j=1}^{n_c} (\text{number of infusions at course } j)$
- Total number of infusions  $\sum_{j=1}^{n_c} (\text{number of infusions at course } j)$
- Cumulative dose over all infusions (g and g/kg):  $\sum_{j=1}^{n_c} \sum_{k=1}^{n_{I_j}} (\text{dose at infusion } k \text{ of course } j)$ , with  $n_{I_j}$  the number of infusions at course  $j$  of the patient

- Average dose per course (g and g/kg):  $\frac{1}{n_c} \sum_{j=1}^{n_c} \sum_{k=1}^{n_{Ij}}$  (dose at infusion  $k$  of course  $j$ )
- Maximum dose over all infusions (g and g/kg)
- Maximum flow rate over all infusions (mL/kg/h)

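### The primary responder definition counts any shorter interval between courses as a treatment change, so read literally a stable patient dosed within the allowed window can be a non-responder

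*SAP*

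**What the plan says.** Response at the end-of-study visit needs two things: an adjusted INCAT score no more than 1 point above baseline, and no change in CIDP treatment (SAP 2.5.1, repeated in 4.6.1). Any one of four conditions is a change:

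- The dose item has a threshold: "Increase/decrease of the dose (g/kg) of the study treatment by 5" per cent.
- The interval item reads, in full, "Decrease of the time between courses".
- The corticosteroid and immunosuppressant item sets a dose and duration for corticosteroids and goes to manual review: "As this condition is not possible to derive by programming, the study physician will review all treatments with corticosteroids and immunosuppressive drugs" before database lock.
- The discontinuation item requires insufficient response and the start of another CIDP treatment.

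On timing, protocol 3.1.4 gives courses "every 3 weeks (+/- 7 days) for a total of 16 doses". SAP 4.5 counts a course as compliant on timing when "Time since previous course = 3 weeks" plus or minus 7 days. SAP 4.5 also defines a prescribed regimen, which "refers to the treatment dose and frequency reported at each IMP course and infusion", but the interval item does not use that term.

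Protocol 3.1.6 lists the treatment changes that can make a 1-point worsening a relapse: "increase in IVIg dosage, increase or initiation of a corticotherapy, immunosuppressive therapy, plasma exchange". A shorter interval is not named there, nor in the responder definition of protocol 3.2.1.

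**The concern.** The same 18-day interval is compliant under SAP 4.5 and, on the plain words of SAP 4.6.1, enough by itself to make the patient a non-responder. Nothing in either document ties the 7-day window to the response definition. The item does not say whether the interval is actual or prescribed, what it is compared with, how often it must occur, or why.

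The primary result is one proportion, with an exact confidence interval, in an expected 15 to 30 patients and no control arm. On the literal reading, appointment timing could be reported as loss of response to the reduced dose. Repeating the analysis on the PPS would not remove the problem: an interval inside the window is not a timing deviation, and the responder definition is the same.

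**Working it through.** **Inputs.** 16 courses, 21 days apart, ± 7 days (protocol 3.1.4); expected N of 15 to 30 (protocol 12.3); Clopper-Pearson 95% interval (SAP 4.6.1). The plan states no expected response rate, so there is no figure to reproduce. The schedule is consistent: 16 courses give 15 intervals, and 15 × 3 = 45 weeks, the stated treatment period.

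**1. The two rules on one patient.** Allowed intervals run from 21 − 7 = 14 to 21 + 7 = 28 days, so those that are both allowed and shorter than planned are 14 to 20 days. Suppose visit 5, planned for day 84, is given on day 87, and visit 6 is given on schedule on day 105. The interval is 105 − 87 = 18 days: compliant under SAP 4.5, a treatment change under SAP 4.6.1 read literally. Protocol 7.2 can itself cause this, since loop diuretics in the preceding 24 hours require postponement. If the comparison is instead with the patient's previous interval, a 28-day interval followed by the planned 21 days is also a decrease.

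**2. Size per patient.** Each patient wrongly counted lowers the rate by 100/N points: 6.7 at N=15, 5.0 at N=20, 3.3 at N=30. The Clopper-Pearson limits are the 2.5% quantile of Beta(x, n−x+1) and the 97.5% quantile of Beta(x+1, n−x). With an assumed true rate of 60%:

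| N | True count | One patient misclassified |
|---|---|---|
| 15 | 9/15 = 60.0% (32.3 to 83.7) | 8/15 = 53.3% (26.6 to 78.7) |
| 30 | 18/30 = 60.0% (40.6 to 77.3) | 17/30 = 56.7% (37.4 to 74.5) |

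**3. How often: assumptions only.** Let q be the chance that a course is one day off schedule, half early and half late, over n intervals. The chance of at least one interval under 21 days is:

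- (a) next course re-set to 21 days after the actual one: 1 − (1 − q/2)^n
- (b) site returns to the calendar week: 1 − Σ over j = 0 to n of (1 − q)^(n−j) (q/2)^j

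| q | (a) n=15 | (b) n=15 | (a) n=7 | (b) n=7 |
|---|---|---|---|---|
| 2% | 14% | 25% | 7% | 12% |
| 5% | 32% | 52% | 16% | 28% |
| 10% | 54% | 78% | 30% | 49% |

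The n=7 columns (8 courses) are shown because SAP 4.10 reports early termination. If courses are only ever late and always re-set, a short interval is forced only after more than 7 late days in total. At q = 10% that has probability P(Binomial(15, 0.10) > 7), about 0.00003. The range is therefore essentially 0 to 78%, depending on site habits that the documents do not describe.

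**4. Would a 14-day cut-off be enough?** Protocol 8.2.2 to 8.2.4 set the visit windows around calendar weeks. Visit 5 at +5 days (day 89) and visit 6 at −3 days (day 102) are both in window but 102 − 89 = 13 days apart. Automatic failure below 14 days would still penalise scheduling.

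**The case against.** The strongest reply is that the item defines a change of treatment, and the treatment is itself a course every 3 weeks within a week either way. A course inside that window delivers the regimen and does not alter it. The neighbouring items all describe changes of therapy, and SAP 4.5 already separates planned from prescribed frequency. A shorter interval can also be hidden intensification: at 14 days the dose intensity for that cycle is 21/14 = 1.5 times planned, so the item has a legitimate purpose. This stands as an account of the likely intent.

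The literal rule would also give results hard to miss. If intervals varied around 21 days with an SD of only half a day, rounded to whole days, about 93% of completers would have a short one. The pre-lock data review (protocol 12.2), the deviation review (SAP 3.5.2) and the statistical review (SAP 5.4) might well catch that. But none of these is described as adjudicating response, and the only item sent to a physician is the one the SAP says cannot be programmed. A programmer given the remaining items could reasonably work from course dates. The "Average course frequency" in SAP 4.7.1 is computed from them, although that is an exposure summary and does not settle how response is derived.

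Two stronger inferences are not supported. A reader might conclude that the responder rate will be substantially understated; no interval data are given, and every frequency above is assumed. A reader might also suspect that the early termination reflects this item. SAP 4.10 attributes it to CIDP relapse, and the relapse definition in SAP 4.6.2 does not use course intervals.

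**Conclusion.** The point holds as a defect in the written rule. Applied as worded, the primary definition fails stable patients whose dosing the protocol and SAP 4.5 accept. The intended meaning is probably narrower, but the text does not secure it, and leaving the choice of reading until results are known is undesirable in an open-label study whose outcomes have already been looked at.

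The direction is certain: the error can only lower the responder rate. The size is certain only per patient, 3.3 points (N=30) to 6.7 points (N=15), against 95% intervals about 37 to 51 points wide at an assumed 60% rate. The number of patients affected is unknown. The study is descriptive with no hypothesis test, and time to relapse and change in INCAT score do not depend on the item. It is worth correcting because it sits in the primary endpoint and the correction is small.

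**What to change.** In SAP 2.5.1 and 4.6.1, replace the interval item with: *a deliberate shortening of the prescribed course interval below the protocol regimen because of insufficient CIDP control; scheduling variation within the protocol visit windows is not a change.*

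Then, before database lock:

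- List all intervals under 21 days from the recorded course dates, marking those under 14 days.
- Have the study physician flag which are treatment changes, as already planned for corticosteroids. No interval should fail a patient automatically.
- Report the responder rate with and without patients who fail on this item alone, that is, counting them as non-responders and then as responders.

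No protocol change is needed. The cost is one wording change, one further physician review and one listing. Course dates are in the eCRF (protocol 6.1.3.3), but the reason for moving an in-window course may not be: the prescription sheet gives planned dates (6.1.2.3), and the reason required for non-compliance concerns dose (6.1.3.4). A shortening whose reason was not documented may therefore go uncounted. The listing of short intervals, read beside the two rates, would show any such patient.

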### 3.4 MULTIPLICITY ISSUES, SUBGROUP ANALYSIS, INTERIM ANALYSIS, BLINDING AND RANDOMISATION

This study is purely descriptive and no hypotheses are tested. No multiplicity issues are present.

No subgroup analyses and no interim analyses are planned.

Likewise, blinding and randomisation is not applicable in this single-arm trial.

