### 3.5 DEFINITION OF THE PROTOCOL DEVIATIONS AND POPULATIONS

#### 3.5.1 Populations

The definition of analysis sets is as follows:

- Total Treated Set (TTS): all patients who received at least one administration of the study drug.
- Full Analysis Set (FAS): all TTS patients having an available assessment of the primary efficacy criterion.
- Per Protocol Set (PPS): all FAS patients without any major deviations from protocol.

If a patient is treated with a non-permitted treatment during the study period, specifically those that confound efficacy evaluation, then all efficacy variables measured after the intake of these not-allowed treatments will be censored for the efficacy analyses. Censoring of measurements will be done up to a reasonable window from the start time of a prohibited treatment where the window is determined according to the half-life of the not- allowed treatment. The window will be adjudicated prior to database lock.

The TTS will be used for the analysis of safety data.

The FAS will be used for the primary analysis of efficacy data and the PPS to test its robustness.

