#### 3.5.2 Protocol Deviations

The protocol deviations and corresponding categories are defined in the protocol deviation specifications as well as their consequence for the inclusion in the different analysis sets. The following protocol deviations categories will be studied:

- Deviations regarding inclusion criteria
- Deviations regarding exclusion criteria
- Deviations regarding the study drug
- Deviations regarding safety assessments
- Deviations regarding assessment of laboratory parameters (including biomarkers)
- Deviations regarding visit windows
- Deviations regarding informed consent
- Deviations regarding forbidden treatments during the study

- Deviations regarding overdose/misuse of study drug
- Other deviations
- Deviations regarding the primary efficacy endpoint
- Deviations regarding other efficacy endpoints
- Deviations regarding exploratory endpoints
- Deviations regarding the ancillary study
- Deviations regarding study material

In addition to these protocol deviations, other protocol deviations may be reported by the clinical research associate (CRA).

All the protocol deviations which occurred during the study will be examined during the final data review meeting. All adjudicated protocol deviations will be presented in data listings.

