#### 4.10 CHANGES IN THE CONDUCT OF THE STUDY OR PLANNED ANALYSIS

Early assessment of study results showed a remarkable percentage of patients who demonstrate CIDP relapse at the tested lower dose. It was decided then to early terminate the study in the interest of the patients and according to good clinical practices. This rationalized the presentation of the efficacy results to focus on key efficacy endpoints.

Results for response rate at 24 weeks, MRC 12 muscles sum score, Rasch-modified MRC sum score, Percentage of patients without change in CIDP treatment from baseline to 24 weeks and EOS visit, and patient and investigator CGI will be presented in listings.

Patient level and course/infusion level information will be provided for exposure, laboratory, and vital signs parameters.

Analysis of laboratory data may involve standardization procedure contingent on the evaluation of the sparseness of laboratory data, the completeness of the local laboratories' normal ranges, and the choice of the standard normal ranges prior to database lock. Liver function test results will be examined to identify Hy's Law, Temple's Corollary, and elevated test result cases.

Analysis of biomarker data will not be performed. Instead the data will be listed using FAS.

Planned analysis associated with the ultrasonography ancillary study will not be performed due to non-collection of required data.

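### The treatment-change flag and the censoring window in the primary endpoint are settled after relapse results were known, with nothing keeping outcome data out of view

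*SAP*

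**What the plan says.** SAP 2.5.1 and 4.6.1 ask two things of a responder: an adjusted INCAT score no more than 1 point above baseline, and unchanged treatment ("The patient's CIDP treatment was not changed between baseline and EOS visit"). One of the four listed kinds of change is "Addition of corticosteroids (equivalent of more than 10 mg/day of prednisone for more than 10 days) or immunosuppressive drugs". The SAP leaves this one to manual review. It gives the reason, "As this condition is not possible to derive by programming", and the procedure: "the study physician will review all treatments with corticosteroids and immunosuppressive drugs prior to database lock and flag those who fulfil the condition".

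SAP 3.5.1 censors efficacy values after a non-permitted treatment, but only up to a window tied to that treatment's half-life: "The window will be adjudicated prior to database lock". Under SAP 4.6.1, a censored EOS score is replaced by the last score before the treatment began.

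On timing, SAP 4.10 reports that "Early assessment of study results showed a remarkable percentage of patients who demonstrate CIDP relapse at the tested lower dose" and that the study was then stopped. On masking, SAP 3.4 says only "Likewise, blinding and randomisation is not applicable in this single-arm trial". Neither document says what the study physician may or may not see during the review, and neither asks for a second assessor.

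**The concern.** Two inputs to the primary endpoint are decided by people at a time when relapse results have been examined: whether a medication course counts as a treatment change, and how long a prohibited treatment blanks out later scores. A decision made before database lock is normally protected because treatment allocation is unknown. In an open-label single-arm study there is no allocation to hide, so the lock date alone protects little. What could bias the decision is sight of the patient's own INCAT course, relapse or reason for leaving, and nothing prevents that.

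At stake is the responder rate, which is the main result. The error could run either way. A borderline course in a stable patient might be flagged, or one in a deteriorating patient left unflagged. The per-protocol repeat would not reveal this, because it uses the same flag and the same windows, and SAP 4.6 runs it only if that set differs from the FAS.

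**Working it through.** **1. Order of events.** SAP 4.10 describes the early assessment and the decision to stop in the past tense. SAP 2.5.1/4.6.1 and 3.5.1 put the flagging and the window decision in the future. So both steps follow knowledge of the results.

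**2. How much judgement the flag leaves.** The corticosteroid part has a numeric threshold for dose and duration. What stays open is conversion to prednisone equivalents, tapering or interrupted courses, partial dates, and addition versus continuation. The immunosuppressant part has no dose or duration limit; SAP 4.6 gives an open-ended list of examples, so which drugs count is also open.

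**3. Which patients depend on the flag.** A patient is a non-responder without it if any of these applies:
- the adjusted INCAT score rose by more than 1 (SAP 4.6.1);
- the patient was withdrawn for insufficient response (SAP 3.2);
- study drug was stopped for insufficient response and another CIDP treatment started (SAP 4.6.1);
- the study-drug dose changed, or the interval between courses shortened, as defined in SAP 4.6.1.

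Protocol 3.1.6 and 5.4 also place the EOS assessment of a relapsing patient before any new CIDP treatment, followed by withdrawal. The flag is therefore decisive only for a patient who meets none of these conditions and received a corticosteroid or immunosuppressant course during the study.

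**4. What the window decides.** Take a hypothetical patient with an adjusted INCAT score of 3 at baseline and 3 at the last visit before a prohibited but unflagged course, and 5 at the scheduled EOS visit.
- Window reaches EOS: 3 is carried forward, the change is 3 − 3 = 0, and the INCAT condition is met.
- Window ends before EOS: the change is 5 − 3 = +2, and the condition fails.

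So the replacement rule in SAP 4.6.1 does not settle the matter by itself. SAP 4.6 also describes censoring after a forbidden treatment with no end point, unlike 3.5.1.

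**5. Size.** The plan has no power or sample-size figure to reproduce: Protocol 12.3 expects 15 to 30 patients with no formal calculation, and the analysis is descriptive. One reclassified patient moves the rate by 100/N points: 100/15 = 6.7, 100/20 = 5.0, 100/25 = 4.0, 100/30 = 3.3.

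The exact limits for x responders of n are the 0.025 quantile of Beta(x, n − x + 1) and the 0.975 quantile of Beta(x + 1, n − x). The documents give no responder rate, so two are assumed: 60%, and about 87%, the complement of the 13% relapse rate on 1 g/kg that Protocol 1.1.2 cites from the placebo-controlled trial with a re-randomised extension.

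| Assumed rate | N | Start | One fewer responder |
|---|---|---|---|
| 60% | 15 | 9/15 = 60.0% (32.3–83.7) | 8/15 = 53.3% (26.6–78.7) |
| 60% | 30 | 18/30 = 60.0% (40.6–77.3) | 17/30 = 56.7% (37.4–74.5) |
| 87% | 15 | 13/15 = 86.7% (59.5–98.3) | 12/15 = 80.0% (51.9–95.7) |
| 87% | 30 | 26/30 = 86.7% (69.3–96.2) | 25/30 = 83.3% (65.3–94.4) |

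In the other direction, 9/15 becomes 10/15 = 66.7% (38.4–88.2). Two fewer responders turn 9/15 into 7/15 = 46.7% (21.3–73.4), and 18/30 into 16/30 = 53.3% (34.3–71.7).

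**The case against.** The strongest reply is that the physician checks every such course against a written condition rather than choosing freely, and that most relapsing patients are already non-responders by the routes in step 3. That stands. It limits the point to edge cases and possibly to no patients at all. It is also true that one patient being worth 1/N holds for any proportion, that a one-patient shift lies well inside the confidence interval, and that no hypothesis is tested, so no error rate is affected. SAP 4.6 adds some transparency by marking assessments after a forbidden treatment in the listings.

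Three stronger readings are tempting, and the documents do not support them.
- A reader might infer that the rule was first written after results were known. The current text postdates the early assessment, but no version history is visible, and Protocol 12.2 already planned a data review before lock.
- A reader might infer that per-protocol membership is likewise decided with outcomes in view, because "All the protocol deviations which occurred during the study will be examined during the final data review meeting". The same SAP section (3.5.2) places the deviation categories, and their consequences for the analysis sets, in separate specifications that are not available here.
- A reader might infer that the physician will in fact see outcomes or misuse the discretion. The documents show only that nothing prevents sight of them.

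The SAP's statement that the condition cannot be programmed can be neither confirmed nor refuted. Protocol 7.2 has all concomitant medication recorded in the eCRF, and SAP 4.4 already handles partial dates by rule, but the dose fields cannot be seen.

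**Conclusion.** The point holds in limited form. Two manual steps that feed the primary endpoint follow knowledge of the relapse results, with no provision to keep outcome data from the person deciding. The risk is bias of unknown direction in a descriptive estimate: 3.3 to 6.7 points for each patient whose status turns on one of these decisions, over the planned 30 to 15 patients. The early stop could leave fewer than 15, and each patient would then weigh more.

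This rests on two assumptions: that some patients received a borderline course or a prohibited treatment, and that they were not non-responders for another reason. The documents do not say how many, and the answer may be none. A cheap improvement is justified because this is the main result; the documents do not show that the result is biased.

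**What to change.** In SAP 2.5.1 and 4.6.1, apply the stated condition by program wherever recorded drug, dose and dates allow, with the prednisone-equivalence table and the list of drugs counted as immunosuppressive written down first. Have the physician classify only the remaining courses, from a medication listing that omits INCAT scores, relapse, responder status and withdrawal reason. Set the SAP 3.5.1 censoring windows from the same listing, and make 3.5.1 and 4.6 agree on whether censoring ends. Sign and date the decisions before they are merged with efficacy data. Report the responder rate twice more, with all disputed courses counted as change and then as no change. If no course is disputed, the two figures coincide and show that the flag did not matter.

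The cost is one extra listing, one form, a short lookup table and two extra proportions. Masking will be imperfect if the physician already knows the patients, so the two bounding figures are worth having even with the stripped listing.
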